#### Obinutuzumab

Patients who experience infusion-related temperature elevations of  $> 38.5^{\circ}\text{C}$  ( $> 101.3^{\circ}\text{F}$ ) or other minor infusion-related symptoms may be treated symptomatically with acetaminophen/paracetamol ( $\geq 500$  mg) and/or H1 and H2 histamine-receptor antagonists (e.g., diphenhydramine, ranitidine). Serious infusion-related events manifested by dyspnea, hypotension, wheezing, bronchospasm, tachycardia, reduced oxygen saturation, or respiratory distress should be managed with additional supportive therapies (e.g., supplemental oxygen,  $\beta$ 2-agonists, and/or corticosteroids) as clinically indicated according to standard clinical practice. For patients enrolled on obinutuzumab-containing regimens, it is recommended that corticosteroids (e.g., 100 mg of IV prednisolone or equivalent) be given as premedication within 12 hours of, but at least 60 minutes prior to, the obinutuzumab infusion on Cycle 1 Day 1. After the first obinutuzumab infusion, additional glucocorticoids are allowed at the investigator's discretion. For patients who did not experience infusion-related symptoms with their previous infusion, premedication at subsequent infusions may be omitted at the investigator's discretion.

Infusion reaction prophylaxis with medications (e.g., acetaminophen/paracetamol, antihistamines, and/or corticosteroids) may be instituted at any point in the study if it is determined to be in the best interest of the patient on the basis of the observation of IRRs in patients already enrolled in the study. Patients with Grade 3 hypotension or fever must be premedicated prior to retreatment.

Patients with hypotension requiring vasopressor support or with Grade 3 wheezing, hypoxia, or generalized urticaria must be permanently discontinued from study treatment.

**Use of the following therapies is prohibited during the study:**

- Cytotoxic chemotherapy
- Radiotherapy
- Immunotherapy including immunosuppressive therapy
- Radioimmunotherapy
- Hormone therapy (other than contraceptives, hormone-replacement therapy, or megestrol acetate)
- Biologic agents (other than hematopoietic growth factors, which are allowed if clinically indicated and used in accordance with instructions provided in the package inserts).
- Any therapy intended for the treatment of lymphoma

Patients who require the use of any of these agents will be discontinued from all study treatment.

### 13.11. Warnings

#### **Idelalisib**

**WARNING: FATAL AND SERIOUS TOXICITIES: HEPATIC, SEVERE DIARRHEA, COLITIS, PNEUMONITIS, INFECTIONS, and INTESTINAL PERFORATION**

- Fatal and/or serious hepatotoxicity occurred in 16% to 18% of idelalisib-treated patients. Monitor hepatic function prior to and during treatment. Interrupt and then reduce or discontinue idelalisib as recommended (see *paragraph 13.12*).
- Fatal and/or serious and severe diarrhea or colitis occurred in 14% to 20% of idelalisib-treated patients. Monitor for the development of severe diarrhea or colitis. Interrupt and then reduce or discontinue idelalisib as recommended (see *paragraph 13.12*).
- Fatal and/or serious pneumonitis occurred in 4% of idelalisib-treated patients. Monitor for pulmonary symptoms and bilateral interstitial infiltrates. Interrupt or discontinue idelalisib as recommended (see *paragraph 13.12*).
- Fatal and/or serious infections occurred in 21% to 48% of idelalisib-treated patients. Monitor for signs and symptoms of infection. Interrupt idelalisib if infection is suspected (see *paragraph 13.12*).
- Fatal and serious intestinal perforation can occur in idelalisib -treated patients across clinical trials. Discontinue idelalisib for intestinal perforation (see *paragraph 13.12*).

#### **Obinutuzumab**

**WARNING: HEPATITIS B VIRUS REACTIVATION and PROGRESSIVE MULTIFOCAL LEUKOENCEPHALOPATHY**

- Hepatitis B Virus (HBV) reactivation, in some cases resulting in fulminant hepatitis, hepatic failure, and death, can occur in patients receiving CD20-directed cytolytic antibodies, including obinutuzumab. Screen all patients for HBV infection before treatment initiation. Monitor HBV-positive patients during and after treatment with obinutuzumab. Discontinue obinutuzumab and concomitant medications in the event of HBV reactivation (see *paragraphs 13.5 and 13.12*).
- Progressive Multifocal Leukoencephalopathy (PML) including fatal PML, can occur in patients receiving obinutuzumab (see *paragraphs 13.5 and 13.12*).

### 13.12. Dose modification and Toxicity Management

#### **Idelalisib**

See Table and paragraphs below for dose modification instructions for specific toxicities related to idelalisib. For other severe or life-threatening toxicities related to idelalisib, withhold drug until toxicity is resolved. If resuming idelalisib after interruption for other severe or life-threatening toxicities, reduce the dose to 100 mg twice daily. Discontinue idelalisib permanently for recurrence of other severe or life-threatening idelalisib-related toxicity upon rechallenge.

No dose modification is required for lymphocytosis, which has been observed in some patients taking idelalisib. This observed lymphocytosis is a pharmacodynamic effect and should not be considered progressive disease in the absence of other clinical findings.

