## Dose Modifications for Toxicities Due to Zydelig

Pneumonitis	Any symptomatic pneumonitis		
	Discontinue Zydelig in patients with any severity of symptomatic pneumonitis		
ALT/AST	>3-5 × ULN	>5-20 × ULN	>20 × ULN
	Maintain Zydelig dose. Monitor at least weekly until <1 × ULN.	Withhold Zydelig. Monitor at least weekly until ALT/AST are <1 × ULN, then may resume Zydelig at 100 mg BID.	Discontinue Zydelig permanently.
Bilirubin	>1.5-3 × ULN	>3-10 × ULN	>10 × ULN
	Maintain Zydelig dose. Monitor at least weekly until <1 × ULN.	Withhold Zydelig. Monitor at least weekly until bilirubin is <1 × ULN, then may resume Zydelig at 100 mg BID.	Discontinue Zydelig permanently.
Diarrhea*	Moderate diarrhea	Severe diarrhea or hospitalization	Life-threatening diarrhea
	Maintain Zydelig dose. Monitor at least weekly until resolved.	Withhold Zydelig. Monitor at least weekly until resolved, then may resume Zydelig at 100 mg BID.	Discontinue Zydelig permanently.
Neutropenia	ANC 1.0 to <1.5 ·10^9/L	ANC 0.5 to <1.0 ·10^9/L	ANC <0.5 ·10^9/L
	Maintain Zydelig dose.	Maintain Zydelig dose. Monitor ANC at least weekly.	Interrupt Zydelig. Monitor ANC at least weekly until ANC ≥0.5 Gi/L, then may resume Zydelig at 100 mg BID.
Thrombocytopenia	Platelets 50 to <75 ·10^9/L	Platelets 25 to <50 ·10^9/L	Platelets <25 ·10^9/L
	Maintain Zydelig dose.	Maintain Zydelig dose. Monitor platelet counts at least weekly.	Interrupt Zydelig. Monitor platelet count at least weekly. May resume Zydelig at 100 mg BID when platelets ≥25 Gi/L.
Infections	Grade 3 or higher sepsis or pneumonia		
	Interrupt Zydelig until infection has resolved.		
	Evidence of CMV infection or viremia		
	Interrupt Zydelig in patients with evidence of active CMV infection of any grade or viremia (positive PCR or antigen test) until the viremia has resolved. If Zydelig is resumed, monitor patients by PCR or antigen test for CMV reactivation at least monthly.		
	Evidence of PJP infection		
	Interrupt Zydelig in patients with suspected PJP infection of any grade. Permanently discontinue Zydelig if PJP infection is confirmed.		

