### **Hepatotoxicity**

Withhold idelalisib in the event of a Grade 3 or 4 aminotransferase elevation (ALT/AST  $\geq 5$  ULN). Once values have returned to Grade 1 or below (ALT/AST  $\leq 3$  ULN), resume idelalisib at 100 mg twice daily.

If the event dose not recur, the dose can be escalated to 150 mg twice daily after consulting with the Medical Monitor. If the event recurs, withhold until return to Grade 1 or below, after which re-initiation may be considered after consulting with the Medical Monitor.

Avoid concurrent use of idelalisib with other drugs that may cause liver toxicity.

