### **Obinutuzumab**

There will be no obinutuzumab dose modification in this study. Consider treatment interruption if patients experience an infection, Grade 3 or 4 cytopenia, or a  $\geq$  Grade 2 non-hematologic toxicity. Any NCI CTCAE (v. 5.0) toxicity Grade  $\geq 3$  in severity that is deemed related to obinutuzumab treatment will require interruption of study treatment until resolution to Grade  $\leq 2$  or  $\geq 80\%$  of baseline, whichever is lower.

Resumption of obinutuzumab treatment may be considered in patients with resolution of toxicities to Grade  $\leq 1$  within 2 weeks at the discretion of the investigator, after consultation with the Medical Monitor. Failure of such toxicities to resolve after 2-week delay in study treatment will require permanent discontinuation of obinutuzumab.

Continuation of study treatment following dose delays beyond 2 weeks will require consultation with and approval of the Medical Monitor based on an assessment of the benefit-risk analysis of continuing to delay study treatment.

Patients in whom toxicities have not resolved (i.e., to Grade  $\leq 1$  or  $\geq 80\%$  of baseline) may have their study treatment delayed by up to 2 weeks. If all study drug-related toxicities have resolved to Grade  $\leq 1$  or  $\geq 80\%$  of baseline, the patient may resume idelalisib and obinutuzumab dosing on the regular every-28-day schedule.

Patients who do not fulfill the criteria for dosing after the additional 2 weeks have elapsed may be discontinued from study treatment and be followed for safety outcomes. Exceptions on the basis of ongoing clinical benefit may be allowed following a careful assessment and discussion of risk versus benefit with the patient by the investigator and approval from the Medical Monitor. In addition, delay of therapy because of toxicities not attributed to study drug may not require discontinuation and will be discussed with the Medical Monitor.

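### Section 13.12 gives opposite idelalisib instructions after ALT/AST above 20 times ULN: the table stops the drug for good, the Hepatotoxicity paragraph restarts it, and no rule says which prevails

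*Combined protocol and SAP*

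**What the plan says.** The idelalisib part of Section 13.12 begins: "See Table and paragraphs below for dose modification instructions for specific toxicities related to idelalisib". A table and a set of paragraphs by toxicity follow.

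The ALT/AST row of the table has three columns. Above 3 and up to 5 times ULN, the dose is maintained. Above 5 and up to 20 times ULN, the entry is "Withhold Zydelig. Monitor at least weekly until ALT/AST are <1 × ULN, then may resume Zydelig at 100 mg BID". Above 20 times ULN, it is "Discontinue Zydelig permanently".

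The Hepatotoxicity paragraph of the same section says "Withhold idelalisib in the event of a Grade 3 or 4 aminotransferase elevation" and defines that range in brackets as 5 times ULN or more, with no upper limit. "Once values have returned to Grade 1 or below", defined in brackets as 3 times ULN or less, the instruction is to "resume idelalisib at 100 mg twice daily". If the event does not come back, "the dose can be escalated to 150 mg twice daily after consulting with the Medical Monitor". If it does come back, the drug is withheld again and re-initiation may be considered, also after consulting the Medical Monitor. The paragraph contains no permanent stop for ALT/AST.

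**The concern.** After ALT/AST above 20 times ULN, one site can read the table and stop idelalisib permanently. Another can read the paragraph and restart it at 100 mg twice daily on its own decision. Each can point to an operative instruction in Section 13.12. Section 13.11 carries a warning of fatal and/or serious hepatotoxicity with idelalisib, so a rechallenge that the same section elsewhere forbids is a patient-safety matter.

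Uniform practice is unlikely to develop unaided. The synopsis plans 12 sites for 43 patients, fewer than four per site on average (43 / 12 = 3.6), and Section 20.1 says that monitoring is done mostly by e-mail and telephone.

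**Working it through.** No formula applies, and the plan states no figure to reproduce on this point. The check sets the two texts side by side and then looks for a rule that decides between them.

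| ALT/AST | Table | Hepatotoxicity paragraph | Compatible? |
|---|---|---|---|
| Above 20 times ULN | Permanent stop | Withhold, then resume at 100 mg twice daily at or below 3 times ULN | No |
| Above 5 and up to 20 times ULN | Withhold; may resume at 100 mg twice daily below 1 times ULN | Withhold; resume at 100 mg twice daily at or below 3 times ULN | Only if the site waits for the lower value |
| Exactly 5 times ULN | Maintain dose | Withhold | No, but a boundary detail |

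**First row.** The paragraph names Grade 4 and gives its own open-ended range, so no outside grading table is needed to see that values above 20 times ULN fall within it. A patient cannot be both permanently off the drug and restarted. The Medical Monitor appears in the paragraph only for the return to 150 mg and for re-initiation after recurrence, so the first restart needs no central approval.

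**Second row.** A patient who recovers to between 1 and 3 times ULN is kept off idelalisib by the table and restarted by the paragraph. The restart dose is the same.

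**Search for a deciding rule:**

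- Section 13.11 refers liver toxicity to Section 13.12 as a whole and does not choose between table and paragraph.
- The fallback at the start of Section 13.12 covers only toxicities not specifically listed, and ALT/AST is listed.
- Section 14.1 provides for stopping on unacceptable toxicity but sets no ALT/AST level.
- The 24-hour reporting rules in Section 16.3 for serious events and events of special interest concern notification, not restart.

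None of these resolves the contradiction.

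**The case against.** The strongest reply is that the table row is the more specific text. The paragraph never mentions 20 times ULN, so a careful reader would let the row limit the paragraph, and a site that restarted would breach an explicit stop. That reading is sensible, but the protocol does not state it. The paragraph expressly includes Grade 4, has no ceiling and is worded as an instruction to resume.

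A second reply is that the restart thresholds are not truly opposed: a patient below 1 times ULN is also below 3 times ULN, so waiting satisfies the table and still meets the paragraph's recovery condition. This largely stands, and it is why the threshold is the lesser point. It remains an inconsistency because the paragraph directs a restart that the table withholds.

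A third reply lists safeguards: Medical Monitor consultation, rapid reporting of serious events and of combined ALT/AST and bilirubin or jaundice cases, and DSMB safety review about every 3 months. They inform the sponsor quickly, but none comes before a first restart.

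Two stronger readings are tempting and not supported:

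- A reader might infer a third conflicting rule from the obinutuzumab text, "the patient may resume idelalisib and obinutuzumab dosing on the regular every-28-day schedule". That sentence concerns the timing of cycles after a treatment delay. Its silence on a reduced idelalisib dose does not override the idelalisib rules.
- A reader might infer that the threshold of 1 times ULN is an error because Section 11.2 admits patients with ALT/AST up to 2.5 times ULN. Whether that threshold suits such patients is a design preference, separate from the disagreement between the two texts.

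**Conclusion.** The contradiction above 20 times ULN is real and stands in the current text. It rests on two readings: that the opening sentence makes table and paragraphs equally operative, and that the paragraph's range of 5 times ULN or more means what it says. The restart threshold after elevations above 5 and up to 20 times ULN is a secondary inconsistency.

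Its frequency cannot be given. Section 7.2 reports 13% transaminase elevations of Grade 3 or higher with idelalisib alone in indolent lymphoma, and a reader might infer about 43 x 0.13 = 5.6 affected patients. That figure counts all such elevations in another population. It does not count values above 20 times ULN or patients whom sites would treat differently. The 16% to 18% in Section 13.11 describes fatal and/or serious hepatotoxicity, which is a different quantity again. The importance of the point rests on the consequence for a patient, not on a count.

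A reader might also infer a statistical defect. There is none: alpha, power, the sample size of 43 and the definition of the primary endpoint are unaffected. Stopping idelalisib does not remove a patient from the analysis, because Section 17.3 includes everyone who received at least one dose.

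**What to change.** Amend Section 13.12 as follows:

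1. Limit the withhold-and-resume text of the Hepatotoxicity paragraph to ALT/AST above 5 and up to 20 times ULN, and state there that above 20 times ULN idelalisib is permanently discontinued.
2. Give one restart threshold in both the table and the paragraph, chosen by the sponsor against the Investigator's Brochure.
3. Add one sentence: where the table and a paragraph differ on whether idelalisib must be stopped, the stricter stop rule governs. This sentence should not be read as setting a restart threshold or dose.

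Until the amendment is approved, sites should follow the stricter text, so that no patient restarts after ALT/AST above 20 times ULN. Interim advice should not relax the table's threshold of 1 times ULN, because Section 22.7 requires approval or advice before a change unless safety overrides.

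The same amendment could, optionally, tidy other differences between the idelalisib texts:

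- **Diarrhea:** the table stops the drug permanently for life-threatening cases, while the paragraph resumes it after Grade 3 or 4, at a dose stated per day where the table gives it twice daily. The stop rules conflict only if Grade 4 means life-threatening, and the grading text is not reproduced.
- **Pneumonitis:** the paragraph's restart, subject to the Medical Monitor, can be read as an exception to the table.
- **Infection:** the triggers in the table, the Serious Infections paragraph and Section 13.11 differ in breadth but do not contradict one another.

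The cost is a wording amendment that needs Ethics Committee and Competent Authority approval or advice under Section 22.7, and slightly fewer idelalisib rechallenges. Section 10.1 still allows obinutuzumab to continue alone where that is judged beneficial. There is no statistical cost.

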## Dose Modifications for Toxicities Due to Zydelig

Pneumonitis	Any symptomatic pneumonitis		
	Discontinue Zydelig in patients with any severity of symptomatic pneumonitis		
ALT/AST	>3-5 × ULN	>5-20 × ULN	>20 × ULN
	Maintain Zydelig dose. Monitor at least weekly until <1 × ULN.	Withhold Zydelig. Monitor at least weekly until ALT/AST are <1 × ULN, then may resume Zydelig at 100 mg BID.	Discontinue Zydelig permanently.
Bilirubin	>1.5-3 × ULN	>3-10 × ULN	>10 × ULN
	Maintain Zydelig dose. Monitor at least weekly until <1 × ULN.	Withhold Zydelig. Monitor at least weekly until bilirubin is <1 × ULN, then may resume Zydelig at 100 mg BID.	Discontinue Zydelig permanently.
Diarrhea*	Moderate diarrhea	Severe diarrhea or hospitalization	Life-threatening diarrhea
	Maintain Zydelig dose. Monitor at least weekly until resolved.	Withhold Zydelig. Monitor at least weekly until resolved, then may resume Zydelig at 100 mg BID.	Discontinue Zydelig permanently.
Neutropenia	ANC 1.0 to <1.5 ·10^9/L	ANC 0.5 to <1.0 ·10^9/L	ANC <0.5 ·10^9/L
	Maintain Zydelig dose.	Maintain Zydelig dose. Monitor ANC at least weekly.	Interrupt Zydelig. Monitor ANC at least weekly until ANC ≥0.5 Gi/L, then may resume Zydelig at 100 mg BID.
Thrombocytopenia	Platelets 50 to <75 ·10^9/L	Platelets 25 to <50 ·10^9/L	Platelets <25 ·10^9/L
	Maintain Zydelig dose.	Maintain Zydelig dose. Monitor platelet counts at least weekly.	Interrupt Zydelig. Monitor platelet count at least weekly. May resume Zydelig at 100 mg BID when platelets ≥25 Gi/L.
Infections	Grade 3 or higher sepsis or pneumonia		
	Interrupt Zydelig until infection has resolved.		
	Evidence of CMV infection or viremia		
	Interrupt Zydelig in patients with evidence of active CMV infection of any grade or viremia (positive PCR or antigen test) until the viremia has resolved. If Zydelig is resumed, monitor patients by PCR or antigen test for CMV reactivation at least monthly.		
	Evidence of PJP infection		
	Interrupt Zydelig in patients with suspected PJP infection of any grade. Permanently discontinue Zydelig if PJP infection is confirmed.		

Abbreviations: ALT, alanine aminotransferase; AST, aspartate aminotransferase; BID, twice daily; ULN, upper limit of normal; CMV, cytomegalovirus; PCR: polymerase chain reaction; PJP: *Pneumocystis jirovecii* pneumonia

\*Moderate diarrhea: increase of 4–6 stools per day over baseline; severe diarrhea: increase of  $\geq 7$  stools per day over baseline.

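### Section 13.12 gives conflicting ALT/AST rules for idelalisib: above 20 × ULN the table stops the drug for good, while the Hepatotoxicity paragraph withholds and then resumes it

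*Combined protocol and SAP*

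**What the plan says.** The idelalisib part of section 13.12 (combined protocol and SAP) opens by sending the investigator to two sources at once: "See Table and paragraphs below for dose modification instructions for specific toxicities related to idelalisib".

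The first source is the table of dose modifications for Zydelig. Its ALT/AST row has three bands:

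- Above 3 and up to 5 × ULN: keep the dose and monitor.
- Above 5 and up to 20 × ULN: "Withhold Zydelig. Monitor at least weekly until ALT/AST are <1 × ULN, then may resume Zydelig at 100 mg BID".
- Above 20 × ULN: "Discontinue Zydelig permanently".

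The second source is the Hepatotoxicity paragraph. Its trigger is "Withhold idelalisib in the event of a Grade 3 or 4 aminotransferase elevation", glossed in brackets as ALT/AST of at least 5 × ULN. Its restart condition is "Once values have returned to Grade 1 or below", glossed as at most 3 × ULN, and the restart dose is 100 mg twice daily. If the event does not come back, "the dose can be escalated to 150 mg twice daily after consulting with the Medical Monitor". If it does come back, the drug is withheld again and may be re-initiated after consulting the Medical Monitor. The paragraph contains no permanent stop.

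A further sentence that names idelalisib sits under the Obinutuzumab heading of 13.12. Once all study-drug-related toxicity is at Grade 1 or below, or at 80% of baseline or better, "the patient may resume idelalisib and obinutuzumab dosing on the regular every-28-day schedule". It gives no idelalisib dose and no ALT/AST limit.

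**The concern.** Two mandatory instructions in one section give different orders for the same laboratory value. A site working from the Hepatotoxicity paragraph could restart idelalisib in a patient whom the table excludes from further exposure. That first restart does not require the Medical Monitor; consultation is asked for only before a return to 150 mg or after a recurrence.

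The risk is one the protocol itself highlights. The warning in section 13.11 states: "Fatal and/or serious hepatotoxicity occurred in 16% to 18% of idelalisib-treated patients". It then tells sites to interrupt, reduce or discontinue as section 13.12 recommends, so it relies on the section that disagrees with itself. ALT and AST are measured before every induction cycle and on days 8 and 15 of cycle 1 (section 15.2), so an elevation would bring these rules into use. With 12 sites, identical values could be handled differently. That could also affect the withdrawal rate and oral compliance (section 9.4) and the summary of adverse events leading to discontinuation (section 17.3).

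**Working it through.** The plan states no figure to reproduce here. The check sets the two texts side by side for specific ALT/AST values and then looks for a rule that decides between them.

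| ALT/AST situation | Table | Hepatotoxicity paragraph | Same order? |
|---|---|---|---|
| Exactly 5 × ULN | Maintain (band above 3 and up to 5) | Withhold (5 or more) | No |
| 10 × ULN | Withhold | Withhold | Yes |
| 10 × ULN, fallen to 2 × ULN | Keep withholding (not yet below 1) | Resume at 100 mg twice daily (3 or less) | No |
| 25 × ULN | Discontinue permanently | Withhold, then resume at 100 mg twice daily at 3 × ULN or less | No |

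**Does the paragraph really reach above 20 × ULN?** Yes. The documents do not print the CTCAE cut-off for Grade 4, but it is not needed. The bracketed trigger of at least 5 × ULN has no upper limit, so 25 × ULN falls inside it.

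**Size of the restart gap.** Upper restart level in the paragraph divided by the limit in the table: 3 × ULN / 1 × ULN = 3. After a hold, any value from 1 to 3 × ULN gets opposite instructions.

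**Is there a tie-breaker?**

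- The opening of 13.12 names the table and the paragraphs together and ranks neither.
- Section 13.11 refers back to 13.12.
- The idelalisib part of 13.12 ends by pointing to Appendix E or the Investigator's Brochure for more detail. Appendix E lists expected serious reactions and has no dosing rule.
- Section 14.1 lets the investigator stop for unacceptable toxicity, but does not require a stop at a given ALT/AST level.

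No precedence statement was found.

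**Context on frequency.** Section 7.2 reports Grade 3 or higher transaminase elevation in 13% of 125 patients in the cited single-agent study: 125 × 0.13 = 16.25, about 16 patients. If the same 13% applied to the 43 patients planned here, 43 × 0.13 = 5.59, about 6. That is an assumption: idelalisib was given until progression or withdrawal in that study and is given for 24 weeks here, with obinutuzumab. Both counts cover any Grade 3 or higher elevation. The share above 20 × ULN is not documented and is not estimated.

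**The case against.** The best defence is that the table and the paragraphs are meant to be applied together. On that reading the explicit band above 20 × ULN is the more specific rule, and a permanent stop leaves nothing to resume. This is a sensible and safe reading, but the protocol does not state it. The paragraph is the dedicated liver text, names Grade 4, and tells the site to resume.

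Other safeguards exist. Bilirubin has its own hold and stop rules in the table. ALT/AST above 3 × baseline with raised bilirubin or jaundice must be reported within 24 hours (section 16.3). Enrolment can stop for Grade 3 or higher non-hematological toxicity (section 17.2), and the DSMB reviews safety about every 3 months (section 18). These lower the chance of harm going unnoticed, but none decides whether an individual patient above 20 × ULN restarts.

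Three points about weight stand. The disagreement at exactly 5 × ULN is minor. The sentence under Obinutuzumab is a general rule for dose delays, and its standing against the liver rules is unclear rather than a further demonstrated conflict. The 16% to 18% in the warning covers all fatal and/or serious hepatotoxicity, not only the patients affected here.

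It can also be said that a liver-only correction is too narrow. For life-threatening diarrhea and for symptomatic pneumonitis the table discontinues, while the matching paragraphs allow resumption. That is true, and it shows that the paragraphs cannot be assumed merely to restate the table. It does not weaken the liver point.

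**Conclusion.** The inconsistency is real and should be corrected. Section 13.12 gives two incompatible orders above 20 × ULN, restart levels that differ threefold after a hold, and a minor clash at exactly 5 × ULN, with nothing to say which text governs. The conflict above 20 × ULN carries the weight, because one of the two orders allows rechallenge after a permanent-stop threshold.

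The conclusion rests only on the protocol's wording and needs no assumption about event rates. The number of patients affected is unknown. No effect on the response rate, power or type I error is claimed.

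**What to change.** 1. In the Hepatotoxicity paragraph, limit the hold-and-resume rule, including the return to 150 mg, to ALT/AST above 5 and up to 20 × ULN. State permanent discontinuation above 20 × ULN, as in the table. This also settles the value of exactly 5 × ULN.
2. Give one ALT/AST restart level in both the table and the paragraph. The sponsor should choose it against the Investigator's Brochure. Section 11.2 admits patients with values up to 2.5 × ULN, and higher with liver involvement, so below 1 × ULN may be out of reach for some.
3. Add a sentence saying that the idelalisib-specific liver rules override the general resume rule under Obinutuzumab. This is tidying and less important than the first two.

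While the section is open, the diarrhea and pneumonitis paragraphs could be reconciled with the table in the same way.

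The cost is a short amendment: a few edited sentences and one aligned value. Because it changes a dosing rule, it needs Ethics Committee and Competent Authority approval before use (sections 21.2 and 22.7), although 22.7 makes an exception for overriding safety reasons. Sample size, endpoints and analysis stay as they are.
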